5.2 Secondary Endpoints

ICS and Azithromycin

- “Days alive and out of hospital within 365 days after recruitment” (continuous data: analysis with T-test)Death or “uncontrolled AECOPD tendency”⁷ within 365 days.
- Number of moderate/severe exacerbation within 365 days
- Cumulative dose of inhaled corticosteroids within 365 days
- Cumulative dose of systemic corticosteroids within 365 days
- Change in lung function (Δ FEV1) from baseline to 365 days

5.3 Exploratory

ICS

- Change in blood eosinophils from baseline to 365 days (eosinophilic trajectories)

⁷ ≥ 3 exacerbations within 12 months

- New diagnosis of diabetes mellitus within 365 days
- Change in HbA1c from baseline to 365 days
- Antibiotic-requiring infections within 365 days

ICS and Azithromycin

- Difference in respiratory microbiota abundance and diversity from baseline to 12 months between treatment arms
- Difference in immunological profile including cytokines and chemokines in the upper airways from baseline to 12 months between treatment arms
- Change in COPD-related quality of life (Based on COPD Assessment Test - CAT) from baseline to 365 days
- Number who progress to MRC -dyspnea score from < 3 to ≥ 3 anytime during follow-up (assessed every 3 months).
- Number of admission requiring non-invasive ventilation (NIV) treatment or admissions to intensive care within 365 days
- Mortality within 365 days

5.3 Data analysis

The four treatment groups will be compared in terms of endpoints at inclusion and follow-up visits every 3 months from trial inclusion with standard statistical tests such as t-test (Dichotomous outcomes), chi-squared test, Fisher's exact test, and time-to-event analyses.

Recurrence of AECOPD, the period between index AECOPD and the next AECOPD, and number of admission-requiring NIV treatment within 365 days are analyzed using Fisher's exact test or Chi-

squared test. Time to AECOPD within 365 days and number of hospitalization-requiring exacerbations within 365 days will be analyzed with t-test and Cox proportional-hazards regression model (unadjusted and adjusted). Mortality rate within 365 days will be analyzed with Chi-squared test or Fisher's exact test (unadjusted) and with Cox proportional-hazards regression model (adjusted).

New onset of diabetes during the study period or occurrence of antibiotic-requiring infections within 365 days will be analyzed using Fisher's exact test or Chi-squared test. Changes in lung function, health-related quality-of-life (CAT), and level of dyspnea (MRC) will be analyzed using analysis of variance (ANOVA). The cumulative ICS dose will be analyzed as mean total cumulative dose from recruitment to end of the study period using t-test, Wilcoxon signed-rank test or Mann-Whitney U test.

6. Risks and Side Effects

Possible side effects from the use of ICS (Beclometasondipropionat) according to pro.medicin.dk are:

Common (1-10%): Pharyngitis, Coughing, Hoarseness, Headache, Candidiasis.

Uncommon (0.1-1%): Blurry vision, Dizziness, Tremor.

Rare (0.01-0.1%): Allergic reactions, Angioedema, Bronchospasm.

Very rare (<0.01%): Adrenal insufficiency. Eosinophilic pneumonia. Erythema, purpura. Decrease in bone mineral density. Glaucoma, cataract. Growth retardation.

Unknown prevalence: Disturbed behavior, Aggressiveness, Anxiety, Depression, Hallucinations, Hyperactivity, Hypercorticism.

Possible side effects from the use of Azithromycin according to pro.medicin.dk are:

Very common (>10%): Abdominal pain, diarrhea, flatulence, nausea.

Common (1-10%): Tiredness or weakness. Decreased appetite. Vomiting, taste perversion. Decreased lymphocyte count. Decreased serum bicarbonate. Arthralgia. Headaches, Paresthesia, Dizziness. Skin itching, rash. Visual disturbances.

Uncommon (0.1-1%): Pain. Hepatitis, Oral candidiasis. Dyspnea, Pneumonia, Edema. Eosinophilia, Leukopenia, Neutropenia. Elevated serum bicarbonate, Hyperchloremia, Hyperglycemia, Hyperkalemia, Hyponatremia, Hypokalemia, Hyponatremia. Arthritis, Back Pain. Nervousness, Somnolence. Facial oedema, Dermatitis, Photosensitivity. Candidiasis, Infections. Metrorrhagia, Kidney Pain, Testicular Disease, Vaginitis. Hearing loss, Tinnitus.

Rare (0.01-0.1%): Cholestasis, Liver Impact. Agitation. Acute generalized exanthemata, pustulosis. Allergic reactions, Angioedema, Hypersensitivity.

Unknown prevalence: Fulminant hepatitis, Hepatotoxicity, Hepatic insufficiency, Pancreatitis, Pseudomembranous colitis. Arrhythmias, Extended QT interval, Hypotension, Torsades de pointes tachycardia. Hemolytic anaemia, Thrombocytopenia. Aggravated myasthenia gravis. Aggressiveness, Anxiety, Delirium, Hallucinations, Hyperactivity, Hypesthesia, Seizures, Syncope. DRESS - drug reaction with eosinophilia and systemic symptoms, Erythema multiforme, Stevens-Johnson syndrome, toxic epidermal necrolysis. Anaphylactic reaction. Acute renal failure, Interstitial nephritis.

Sample collection

When drawing a blood sample, there is a small risk of infection, slight discoloration at the puncture site, and transient pain/discomfort. Tracheal aspirate collection is associated with a small risk of minimal bleeding, infection, temporary breathing difficulties, and a low blood oxygen level during the examination. There are no known risks associated with nasosorption sample collection.

Documentation and reporting of adverse events

In the present study, the IMPs are not under stricter reporting requirements as per DKMA list available at webpage (<https://laegemiddelstyrelsen.dk/en/sideeffects/side-effects-of-medicines/medicines-with-stricter-reporting-requirements/>). Furthermore, inhaled corticosteroids (ICS) and azithromycin have extensive market presence, in the specified patient population, both with well-established safety profiles. In addition, the morbidity and mortality within this clinical trial's patient group is very high. Therefore, a risk-based safety reporting will be conducted, meaning only SUSARs will be expedited reported from the investigator to sponsor

All severe adverse events (SAE) will be documented in the electronic case report forms (eCRFs) as soon as the investigators are made aware of the events. Every 3 months at study follow-up visits, the study participants will be asked about SAEs, and the electronic patient files will be assessed for events since last visit. Participants are also advised to contact the investigators during the trial in case they experience an adverse event. Investigators will then immediately assess whether a

causal association to the study drugs is suspected. If the SAE – in the opinion of the investigator - exhibits potential causality with the study drugs, the event will be considered a serious adverse reaction (SAR). This will also be documented in the eCRFs. The investigators will then be prompted to assess if the SAR is expected. If the event is unexpected, as outlined above in the Summary of Product Characteristics for ICS and azithromycin, the investigators will be prompted to report immediately to the sponsor, as this will be considered a SUSAR. SUSARs must reported to sponsor within 24 hours after the study site have been aware of the event, by email or telephone. An immediate report ensures a duly and timely report to the EudraVigilance system if it is deemed to be a SUSAR. In addition to this, the investigator will be able to report any SAE immediately at their own discretion.

The sponsor will ensure prompt registration and reporting through the EudraVigilance system of all information regarding eligible SUSARs that are fatal or life-threatening, no later than 7 days after the sponsor becomes aware. Within 8 days of filing the report, the sponsor must update the EudraVigilance system including all pertinent details regarding the sponsor's and investigator's follow-up on the report. Test managers at other participating centers must be promptly informed of these SUSARs.

SAEs and SARs that do not qualify as SUSARs will not be reported immediately from investigators to sponsor, however these events will all constitute either a primary or secondary outcome according the protocol, and therefore will be registered by investigators in the eCRF. As described previously sponsor will be notified at every 3 months corresponding to study follow-up visits, where the participants will be inquired about events. At any time, the sponsor will be able to assess all registered SAE/SARs via the eCRF.

Events will be considered exclusively within the trial period, encompassing participant enrollment from screening to the last visit day. An annual safety report (ASR) of all SARs and SUSARs occurring during the trial period along with a description of the rules of registration and reporting of adverse events as given in this protocol will be submitted to the Clinical Trials Information System (CTIS). All SAEs, SARs, SUSARs will be reported in the final report to the CTIS at the conclusion of the trial.

7. Exclusion from or interruption of the trial

Participants may at any time terminate the study if the physician responsible for the study deems it necessary with medical justification (allergy to the medicine, safety risk, or other adverse circumstances). The investigator can furthermore at all hours unblind the Azithromycin/placebo treatment by contacting Glostrup Apotek. Termination and unblinding should preferably be done in agreement with the coordinating investigator of the project. The participant in question will be informed immediately of health concerns, project termination, and future treatment plan. Additionally, participants may, at any time, withdraw their informed consent. This will not have any consequence on further treatment.

8. Economy

The initiative for the trial was taken by the steering committee of COP:TRIN (Chronic Obstructive Pulmonary Disease: Trial Network) and the departments of pulmonary medicine at Gentofte Hospital, Herlev Hospital, Hvidovre Hospital, Bispebjerg Hospital, North Zealand Hospital, and Aalborg Hospital. The project budget is approximately DKK 7.433.600. This amount will cover salary to researchers, supervisors, nurses and auxiliary staff, the cost of data collection, equipment, medication, laboratory analyses, diagnostic tests, and potential hospitalizations.

Funding has been sought from various foundations, including Region H Research Fund. The Scientific Ethics Committee and the trial participants will be informed of the sponsors, their financial contribution and its part in the project, and information on grant recipient (Whether the support is paid directly to the investigators or their department/institute).

The Novo Nordisk Foundation has supported the initiative with 4.6 million DKK by a grant to [name].

The investigators have no economic interests in the research project in question and are not financially linked to private companies, foundations etc. with economic interests in the study.

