2.2 Microbiota objectives

ICS

- Whether a strategy of eosinophil-guided administration of ICS in COPD patients with GOLD class E and/or $FEV_1 < 30\%$ leads to a change in (i) the respiratory microbiota abundance and diversity and (ii) the immunological profile in comparison to continuous triple therapy (ICS/LABA/LAMA).

Azithromycin

- Whether prophylactic low dose Azithromycin in COPD patients with GOLD class E and/or $FEV_1 < 30\%$ leads to changes in (i) the respiratory microbiota abundance and diversity and (ii) the immunological profile.

3. Hypotheses

ICS primary

- In COPD patients with GOLD class E and/or $FEV_1 < 30\%$, an eosinophil-guided administration of ICS treatment regimen is associated with no apparent loss of efficiency⁵.

ICS secondary

- In COPD patients with GOLD class E and/or $FEV_1 < 30\%$, eosinophil-guided administration of ICS will reduce the use of inhaled corticosteroids by $> 25\%$ ⁶.

⁵ Measured by "admissions with COPD exacerbation or death from all causes within 365 days

⁶ Measured by budesonide equivalent doses

- In COPD patients with GOLD class E and/or FEV₁ < 30%, eosinophil-guided administration of ICS will reduce the number of ICS related side effects.
- The respiratory microbiota have a composition of less "pathogenic" bacterial species in COPD patients with GOLD class E and/or FEV₁ < 30%, treated with the eosinophil-guided administration of ICS regimen compared to those treated with continuous triple therapy (ICS/LABA/LAMA) regimen.
- The complexity of the respiratory microbiota is lower among COPD patients with GOLD class E and/or FEV₁ < 30%, treated with continuous triple therapy (ICS/LABA/LAMA) regimen than among those treated with the eosinophil-guided administration of ICS regimen.
- The immunological profile of the upper airways changes in COPD patients with GOLD class E and/or FEV₁ < 30% treated with the eosinophil-guided ICS regimen compared to those treated with continuous triple therapy (ICS/LABA/LAMA) regimen.

Azithromycin primary

- In COPD patients with GOLD class E and/or FEV₁ < 30%, the use of low dose Azithromycin can result in a reduction in admissions with COPD exacerbation or death from all causes within 365 days" as compared to placebo.

Azithromycin secondary

- The difference in composition of the respiratory microbiota is substantial when COPD patients with GOLD class E and/or FEV₁ < 30% are treated with prophylactic low dose Azithromycin

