4.1 Study design

COPERNICOS is a 4-arm facultative designed, randomized controlled, multicentre, parallel group, double blinded, non-inferiority intervention study in participants with COPD (GOLD class E and/or $FEV_1 < 30\%$).

Participants will be randomly allocated to one of the following four treatment groups:

[figure not shown]

Figure 1: The four treatment groups (**Control** – **Active**)

1. Eosinophil "Control"/Azithromycin "Control" group:

- Azithromycin: participants are given placebo
- ICS: The participants are given the usual LAMA/LABA/ICS product in the usual dose.

2. Eosinophil "Active"/Azithromycin "Control" group:

- Azithromycin: placebo
- ICS: All participants will receive LABA/LAMA medication. The ICS medication will be switched on/off according to the most recent blood eosinophil count (at inclusion + every 3 months):
 - i. If blood eosinophil $\geq 0.3 \times 10^9$ cells/L, ICS is continued in usual dose next 3 months.
 - ii. If blood eosinophil $< 0.3 \times 10^9$ cells/L, ICS is discontinued.

3. Eosinophil "Control"/Azithromycin "Active" group:

- Azithromycin: 250 mg Azithromycin three times weekly.
- ICS: The participants are given the usual LAMA/LABA/ICS product in the usual dose throughout the entire project period

4. Eosinophil "Active"/Azithromycin "Active" group:

- Azithromycin: 250 mg Azithromycin three times weekly.
- ICS: All participants will receive LABA/LAMA medication. The ICS medication will be switched on/off according to the most recent blood eosinophil count (at inclusion + every 3 months):
 - i. If blood eosinophil $\geq 0.3 \times 10^9$ cells/L, ICS is continued in usual dose next 3 months.
 - ii. If blood eosinophil $< 0.3 \times 10^9$ cells/L, ICS is discontinued.

A microbiological and immunological study within the framework of the randomized study aims to investigate the respiratory microbiota and immunological profile in participants from the four randomized groups. A total of 40 participants from each group will participate in the sub-study and

will undergo tracheal aspirate collection and nasal swabs at baseline and 12 months follow-up. Collection of tracheal aspirates is a routine procedure at participating centres and serious complications are very rare. Nasal swab is not associated with any serious complications. Participants' data and laboratory specimens will be assigned a coded identification number to maintain participant confidentiality.

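### Protocol Section 5.3 (Data analysis) names tests that do not fit some outcomes: a t-test for censored times, contingency tests for an interval and a count, and a paired test for independent arms

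*Protocol*

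**What the plan says.** All the test assignments below are in Protocol Section 5.3 (Data analysis), which follows a Section 5.3 headed Exploratory.

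- General list: "standard statistical tests such as t-test (Dichotomous outcomes), chi-squared test, Fisher's exact test, and time-to-event analyses".
- Interval and NIV count: "the period between index AECOPD and the next AECOPD, and number of admission-requiring NIV treatment within 365 days are analyzed using Fisher's exact test", with chi-squared as the alternative.
- Time to AECOPD and number of admissions: "Time to AECOPD within 365 days and number of hospitalization-requiring exacerbations within 365 days will be analyzed with t-test and Cox proportional-hazards regression model", the Cox model both unadjusted and adjusted.
- Cumulative ICS dose: compared as a mean total "using t-test, Wilcoxon signed-rank test or Mann-Whitney U test".

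Two other places bear on these choices. Section 4.1 describes the trial as "randomized controlled, multicentre, parallel group, double blinded", so the arms are independent. Section 3 (ICS secondary) states that "eosinophil-guided administration of ICS will reduce the use of inhaled corticosteroids by" more than 25%, measured in budesonide equivalents.

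**The concern.** These are methods that the protocol states, not details it leaves to a later document. Several do not match the type of data.

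- **Time to AECOPD.** Anyone without an event is censored at day 365 or earlier. A t-test must either treat the censored time as an event time or drop those participants.
- **Interval between exacerbations.** A duration cannot enter a contingency table without a cut-point, and none is given. The index AECOPD is not defined either.
- **Counts.** Hospitalised exacerbations are given a t-test and Cox, and NIV admissions are given Fisher or chi-squared. None of these is a model for a count over follow-up that may vary.
- **Cumulative ICS dose.** The signed-rank test needs pairs, which parallel arms do not have. With three tests and no selection rule, the choice could be made after the data are seen. A test against zero difference does not by itself address a reduction of more than 25%.
- **The t-test label.** It is attached to dichotomous outcomes.

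At stake are lost power, possible false positives if follow-up differs between arms, and analyses that cannot be run as written.

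**Working it through.** The plan gives no figure on this point to reproduce. The check has two parts: matching test to outcome, and sizing the cases where a number is possible.

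**Matching**

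| Outcome | Data type | Test named | Fit |
|---|---|---|---|
| Time to AECOPD | censored time | t-test and Cox | Cox fits, t-test does not |
| Index-to-next interval | duration, possibly unobserved | Fisher or chi-squared | cannot be run without a cut-point |
| Number of hospitalised exacerbations | count | t-test and Cox | standard Cox does not; t-test ignores follow-up time |
| Number of NIV admissions | count | Fisher or chi-squared | only if reduced to any versus none |
| Cumulative ICS dose | continuous, independent arms | t-test, signed-rank or Mann-Whitney | signed-rank does not; it fails on 222 versus 221 values |

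**Inputs for sizing.** From Section 5: event risks of 30% and 20%, and 222 per side. Those risks are for exacerbation or death and are borrowed for illustration. Assumed: exponential event times, withdrawal unrelated to the event, and the withdrawal rates themselves. Tests are two-sided at 5%.

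**Power for time to AECOPD, 30% versus 20%, no withdrawal**

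The hazard is λ = −ln(1−p)/365, which gives 0.00097719 and 0.00061134 per day.

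1. *t-test on all times, censored counted as events.* Mean = p/λ: 0.30/0.00097719 = 307.0 days and 0.20/0.00061134 = 327.1 days, a difference of 20.1. The SDs under the exponential model are 105.6 and 89.1. SE = √((105.6² + 89.1²)/222) = 9.28, so z = 20.1/9.28 = 2.17. Power = Φ(2.17 − 1.96) ≈ 58%. Simulation (4,000 runs): 57%.
2. *t-test on events only.* Expected events are 0.30×222 = 66.6 and 0.20×222 = 44.4. Mean event times are 171.7 and 175.7 days, with SDs of about 105. SE = √(105.0²/66.6 + 105.2²/44.4) = 20.4, so z = 0.20 and the rejection rate is about 5–6%. Simulation: 6%.
3. *Log-rank (unadjusted Cox score test).* HR = ln 0.80/ln 0.70 = 0.626. With 111 events, z ≈ √(111/4)×0.469 = 2.47, so power is about 70% by this approximation. Simulation: 67%.

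**False positives, no treatment effect, 30% in both arms**

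Withdrawal is uniform over the year in a fraction w of participants. Mean observed time is 307.0 days in those who stay and (1 − 0.30/0.35667)/0.00097719 = 162.6 days in those who withdraw.

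- w = 5%: 0.95×307.0 + 0.05×162.6 = 299.8 days
- w = 15%: 0.85×307.0 + 0.15×162.6 = 285.3 days

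The difference is 0.10×(307.0 − 162.6) = 14.4 days. The SDs are 110.1 and 117.3, so SE = 10.8, z = 1.34 and the rejection rate is about 27%.

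| Withdrawal (assumed) | t-test on all times rejects |
|---|---|
| 5% vs 5% | 5% |
| 8% vs 12% | 8% |
| 5% vs 10% | 10% |
| 5% vs 15% | 27% |
| 5% vs 20% | 51% |

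A separate simulation with exponential dropout of 5% versus 20% gave 53% for this t-test and 5% for log-rank.

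**t-test on a dichotomous outcome.** For 67/222 versus 44/222, p = 0.0116 by t-test and 0.0117 by chi-squared. Simulated type I error at 222 per side is 5.0% versus 5.1%.

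**ICS dose.** A reduction above 25% means a ratio of mean doses below 1 − 0.25 = 0.75. Rejecting equality shows only that the doses differ.

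**The case against.** The strongest reply is that this is loose wording with valid methods already present. Cox is named for time to AECOPD. The t-test and Mann-Whitney are both usable for ICS dose. Chi-squared or Fisher is assigned to the diabetes, infection and unadjusted mortality comparisons. The sentence on time and number could be read as Cox for the first and t-test for the second. A recurrent-event extension of Cox can handle repeated events. An SAP, not seen here, may settle all of this.

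Much of that stands, and it limits the consequence. It does not make the stated tests fit: the two methods are joined by *and*, no recurrent-event extension is named, and nothing says which ICS-dose test governs.

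A reader might infer four stronger things that the protocol does not support.

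- *That the section as a whole yields biased or impossible results.* The dichotomous label is a slip with negligible numerical effect, and the t-test on censored times keeps about 5% type I error when withdrawal is equal. No passage points to 5% versus 15%. The azithromycin comparison is placebo-controlled, and admissions can be taken from health records.
- *That several secondary endpoints are affected.* Time to AECOPD and the interval appear in none of the endpoint lists, and NIV admissions are exploratory. Number of admissions belongs to the primary outcome, which has its own test in Section 5.1. Of the listed secondary endpoints, only cumulative ICS dose is given one of the ill-fitting tests.
- *That a small ICS reduction, such as 10%, would be declared a success.* No success rule is stated, and Section 10 anticipates a reduction of up to 80%.
- *That the interval is necessarily a non-randomised comparison.* This depends on what the index AECOPD is. If it is a qualifying event before entry, there is no selection on a post-randomisation event.

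**Conclusion.** The point holds as a set of specific mismatches between test and outcome. Two of the stated options cannot be run as written: a contingency test on an interval without a cut-point, and a signed-rank test on independent arms. The t-test for time to AECOPD costs power in the illustration (57% or 6% against 67%). It is liable to false positives only if follow-up differs between arms: from 5% with equal withdrawal to about 27% at 5% versus 15%. These sizes rest on exponential times, on the protocol's composite event risks borrowed for AECOPD, and on withdrawal rates that the protocol does not give. Two counts lack a count method. The ICS-dose comparison has an open choice of test and no link to its 25% hypothesis. The dichotomous label needs correcting but changes no result. All of this should be put right before analysis.

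**What to change.** Amend Section 5.3 (Data analysis), or settle the same points in the SAP and refer to it.

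1. Time to AECOPD: delete the t-test and use Kaplan-Meier and Cox. State how death is handled, since the protocol gives no rule for this outcome.
2. Index-to-next interval: remove Fisher and chi-squared, define the index AECOPD, and use a time-to-event or recurrent-event analysis in all randomised participants.
3. Numbers of hospitalised exacerbations and of NIV admissions: use a count model, for example negative binomial with log follow-up time as offset.
4. Cumulative ICS dose: delete signed-rank and prespecify one unpaired analysis. Report the ratio of mean budesonide-equivalent doses (guided over control) with a 95% CI, and claim a reduction above 25% only if the upper limit is below 0.75.
5. Attach the t-test label to continuous outcomes.

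The cost is wording only. The same data are used, with no new visits or participants. The count model is one reasonable choice among several; what matters is that one fitting method is fixed for each outcome before unblinding.

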2.1 Clinical objectives

ICS

- Whether a strategy of eosinophil-guided¹ administration of ICS in COPD patients with GOLD class E and/or FEV₁ < 30% can lead to non-inferior² treatment responses to triple therapy (ICS/LABA/LAMA).
- Whether side effects³ due to ICS exposure can be reduced with the eosinophil-guided administration of ICS.

Azithromycin

- Whether the use of prophylactic low dose Azithromycin⁴ in COPD patients with GOLD risk E and/or FEV₁ < 30% can reduce moderate and severe exacerbations.

¹ Blood eosinophils are measured every 3rd month during the study. If blood-eosinophils < 0.3 x 10⁹ cells/L, ICS treatment will be paused for the next 3 months. If blood-eosinophils are ≥ 0,3 x 10⁹ cells/L, ICS treatment will be continued/resumed during the next 3 months.

² Unchanged number of COPD exacerbations or death from all cause within 365 days

³ New diagnosis of diabetes mellitus, change in HbA1c and antibiotic requiring infections

⁴ 250 mg Azithromycin three times weekly

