4.8 Research Biobank

The purpose of establishing a research biobank is to investigate the frequency of ICS-induced side effects and the changes in respiratory microbiota in different treatment groups. This biobank will clarify the hypotheses and provide biological materials for future research (Providing that future

projects can obtain a separate approval from the Danish National Committee on Health Research Ethics).

The research biobank will store blood samples, tracheal aspirate samples, and nasal swabs. Tracheal aspirate and nasal swab samples are taken from 40 participants from each treatment arm, in total 160 participants. Approximately 1-5 ml of tracheal aspirate will be collected from each participant. Blood samples are taken from each participant at inclusion and at follow-up every 3 months during the 12-month study period. Approximately 210 ml of blood will be collected during the entire study period corresponding to a maximum of 36 ml per blood draw. All samples are stored in a freezer at -80 degrees Celsius. The freezers are kept in a locked room at each of the participating pulmonary medicine departments.

All samples are pseudonymized and kept for 15 years in accordance with present legislation and data protection laws. Establishment of this research biobank ends **31AUG2027**. Following the end of this study and the research biobank, all surplus biological material will be transferred to a future-research biobank. These samples will also be pseudonymized and kept for 15 years. Permission to store biological material from participants in the research biobank and future-research biobank is a part of the informed consent to participation in the project.

5. Statistical Considerations (Power Calculation)

Participants will be randomized using stratified block randomization (REDCap) to ensure equal distribution of participants at the site, age (less than 70 years vs 70 years or more) and number of hospital-requiring exacerbations within the past 12 months (0-1 vs 2 or more).

The trial will have a target of 444 participants, , included in the project within 48 months, and 111 participants will be allocated to each of the four groups to be examined.

Two sample size calculations have been conducted, one for ICS and one for azithromycin, as there are two interventions being tested (factorial design):

A non-inferiority (1-sided) test for ICS.

Type 1 error limit (α) 2.5%, Power ($1-\beta$) of 80%. ($\alpha = 0.025$, $\beta = 0.2$)

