Control group exacerbation/death: 0.3 (30%)

Expected maximum worsening >11% absolute (up to 0.41)

Sample size 444 (222 x 2)

A 1-sided superiority test for azithromycin.

Type 1 error limit (α) 2.5%, Power ($1-\beta$) of 80%. ($\alpha = 0.025$, $\beta = 0.2$)

Control group exacerbation/death: 0.3 (30%)

Expected effect: >10% absolute (up to 0.2)

Sample size 444 (222 x 2)

These two interventions will be published separately in two primary publications, but there will be adjustments in the main analysis to account for whether they received the other intervention. These two analysis teams (separate) will be blinded to an effect estimate of the other intervention.

40 participants from each group will participate in the microbiota sub-study.

Scheduled analyses of data (Interim analysis) will be assessed when half of the participants are recruited. These assessments will be made by the independent Data and Safety Monitoring Board (DSMB) on the two primary endpoints, and for the secondary endpoint “Death or “uncontrolled AECOPD tendency” within 365 days”. Data on primary and secondary power targets will be used for this purpose. DSMB will review the protocol, monitor the guideline, evaluate the trial concerning the recruitment of participants, participants' risk and, based on interim analyses, make recommendations to the investigators on whether to continue or cease the study. DSMB may at any time require an extraordinary interim analysis

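### Antibiotic-requiring infections, an exploratory endpoint but a named measure of the ICS side-effect objective, are tested only as any versus none, which discards repeat infections; how much power this costs depends on an infection rate the protocol does not give

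*Protocol*

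**What the plan says.** Footnote 3 to section 2.1 Clinical objectives defines the side effects that the eosinophil-guided strategy is meant to reduce: "New diagnosis of diabetes mellitus, change in HbA1c and antibiotic requiring infections". Section 3 Hypotheses, under ICS secondary, expects that "eosinophil-guided administration of ICS will reduce the number of ICS related side effects".

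The endpoint list in section 5.3 Exploratory has, for ICS only, "Antibiotic-requiring infections within 365 days". It does not say whether this is a count or a yes/no measure. The form is fixed in section 5.3 Data analysis: "occurrence of antibiotic-requiring infections within 365 days will be analyzed using" Fisher's exact or chi-squared test. The same sentence applies the same tests to new onset of diabetes.

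No infection rate, expected effect, power or alpha is stated for this endpoint. On numbers, section 5 says that "111 participants will be allocated to each of the four groups to be examined", which makes 222 against 222 for the ICS comparison.

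**The concern.** A person can become newly diabetic only once, so a 2x2 table loses little there. Infections can recur, and section 1 describes COPD patients as prone to frequent lower respiratory infections. Three things follow from testing only whether an infection occurred:

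- A participant with four infections counts the same as one with a single infection.
- Someone who dies or withdraws early without an infection counts the same as someone infection-free for 365 days. The adverse-event text in section 6 describes morbidity and mortality in this group as very high.
- An unadjusted 2x2 test cannot take account of azithromycin allocation, although half of each ICS side receives an antibiotic. Section 5 promises adjustment for the other intervention in the main analysis.

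At stake is the sensitivity of the only infection outcome among the three side-effect measures. No reason is given for the yes/no form.

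**Working it through.** **The plan's own figure.** There is none to reproduce for this endpoint. The only planning number used is the group size: 4 x 111 = 444, so 222 per side for ICS.

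**Assumptions (not in the documents).** Counts per participant over one year are negative binomial with control mean m, dispersion k and rate ratio r. The same rate ratio applies to first and later infections, follow-up is complete, and the test is two-sided 5% with n = 222 per side.

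**Any versus none.** P(at least one) = 1 - (1 + km)^(-1/k), or 1 - exp(-m) when k = 0. Power = Φ[(d - 1.96·s0)/s1], where d is the difference in proportions, s0 its pooled standard error and s1 its unpooled standard error.

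**Count.** SE of the log rate ratio = √[(1/m + 1/(rm) + 2k)/n]. Power = Φ[|ln r|/SE - 1.96].

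**Worked case: m = 1, k = 1, r = 0.75.**
- Proportions: 1 - 1/2 = 0.500 and 1 - 1/1.75 = 0.429, so d = 0.0714; s0 = 0.0473, s1 = 0.0472. (0.0714 - 1.96 x 0.0473)/0.0472 = -0.45, so power is 33%.
- Count: SE = √[(1 + 1.333 + 2)/222] = 0.1397; 0.2877/0.1397 = 2.06; 2.06 - 1.96 = 0.10, so power is 54%.

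**Other cases.**

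| m per year | k | r | With ≥1 infection | Any vs none | Count | Gain (points) |
|---|---|---|---|---|---|---|
| 0.5 | 0 | 0.80 | 39% vs 33% | 28.7% | 34.7% | 6.0 |
| 1.0 | 1 | 0.75 | 50% vs 43% | 32.6% | 53.9% | 21 |
| 1.5 | 1 | 0.75 | 60% vs 53% | 32.2% | 62.3% | 30 |
| 1.5 | 0.5 | 0.75 | 67% vs 59% | 44.2% | 76.5% | 32 |
| 2.0 | 0 | 0.80 | 86% vs 80% | 46.5% | 88.0% | 41.5 |

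**Grid.** With m = 0.5, 0.75, 1, 1.5, 2; k = 0, 0.5, 1, 1.5; and r = 0.70, 0.75, 0.80 (60 combinations), the gain runs from 6.0 to 41.5 points, median 19.

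**Outside the grid (k 0 to 1.5).**
- m = 0.3, r = 0.80: gain 2.3 to 3.2 points.
- m = 0.5, r = 0.85: gain 3.6 to 3.7 points.
- m = 0.5, r = 0.90: gain 1.6 to 1.7 points.
- m = 1, k = 1, r = 0.90: 8.0% to 11.8%, gain 3.8 points.

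**Simulation check (2,000 trials per scenario, robust rate ratio for the count).** At m = 1, k = 1, r = 0.75: chi-squared 33.7%, Fisher 30.1%, count 54.0%. At m = 2, k = 0.5, r = 0.75: 45.0%, 40.1% and 81.7%. Fisher, the other permitted test, loses about 3 to 5 points more than chi-squared. The count analysis had more power in every scenario tried.

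**The case against.** The strongest reply is about weight. The endpoint is exploratory, no power is claimed for it, and no primary or secondary conclusion depends on it. The size of the loss rests wholly on assumed rates, and with few infections or a weak effect it is trivial. All of that stands.

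Four stronger readings are tempting, and the documents do not support them.

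- *A missed effect here would undo the case for eosinophil guidance.* That case rests on the non-inferiority result and the hypothesised reduction of more than 25% in ICS use. HbA1c and new diabetes are separate side-effect measures. In the worked case the count analysis itself has only 54% power.
- *Nearly everyone will have an infection, so the yes/no measure saturates.* The inclusion criteria concern exacerbations and FEV1, not infection rates, and the worked case has 50% against 43%.
- *The analysis contradicts the hypothesis because that speaks of a number.* The wording covers all side effects together, including diabetes, which occurs once. It is loose support for a count, not a contradiction.
- *The loss is always material.* It is only 2 to 4 points in the low-rate or weak-effect cases above.

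There is also a practical objection. The protocol defines no infection episode, and its three-monthly enquiry is described for serious events: "Every 3 months at study follow-up visits, the study participants will be asked about SAEs". Any versus none is less sensitive to confusing a prolonged course with a new infection, and the power comparison does not reflect this. That is a reason to set a counting rule; it does not make the yes/no test preferable.

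**Conclusion.** The concern holds in limited form. The protocol itself fixes a yes/no test for a repeatable event that it names as a measure of a stated objective, so this is not a detail left to an analysis plan. The test discards repeat infections, ignores unequal follow-up and cannot adjust for azithromycin.

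If control infections run at 0.5 to 2 per year with a true rate ratio of 0.70 to 0.80 and dispersion up to 1.5, the cost is about 6 to 41 points of power, typically about 19. The top of that range requires 2 per year and no between-patient variation. At 0.3 per year with rate ratio 0.80, or 0.5 per year with rate ratio 0.85 to 0.90, it is about 2 to 4 points. The direction did not reverse in any case examined. The effect is confined to an exploratory endpoint.

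**What to change.** In section 5.3 Data analysis, separate infections from new-onset diabetes. Compare the number of antibiotic-requiring infections per participant within 365 days of randomisation by negative binomial regression, with log time at risk as offset and terms for azithromycin allocation and the stratification factors (site, age group, prior hospital-requiring exacerbations). Report the rate ratio with its 95% confidence interval. Keep the proportion with at least one infection as a descriptive result, and keep Fisher or chi-squared for new-onset diabetes.

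The cost is a wording change plus a rule for distinct episodes, based on treatment start dates, so that repeated or prolonged courses for one infection count once. Those dates must be captured; section 4.2 already allows medication and admissions to be read from health files. No extra patients or visits are needed. A rate ratio is slightly harder to present than a percentage. The offset corrects for length of observation but does not remove bias from informative death, so deaths by arm should be shown alongside.
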